6.7.1. Protocol Permitted Substitutions

6.7.1.1. Oral Bridging

In exceptional circumstances, to address pre-planned missed CAB LA + RPV LA dosing visits, in consultation with the medical monitor, Investigators may provide daily oral CAB 30 mg and RPV 25 mg as a short-term “bridging” strategy for participants who have begun CAB LA + RPV LA. In certain circumstances (e.g., prior to steady state dosing and following a >4 week oral bridge) repeating the loading doses of CAB IM and RPV IM may be required. Should a participant require “oral bridging”, sites must contact the study Medical Monitor for guidance with treatment and dosing strategies prior to a missed CAB LA + RPV LA dose.

Please refer to [Appendix 10](#) in Section 12.10 for study management information during the COVID-19 pandemic.

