#### 12. APPENDICES

# 12.1. Appendix 1: Protocol Deviation Management and Definitions for Per Protocol Population

#### 12.1.1. Exclusions from Per Protocol Population

Important protocol deviations leading to exclusion from the Per Protocol population are those deviations which may

- i. directly impact the efficacy endpoint of HIV-1 RNA; or
- ii. lead to permanent discontinuation of IP/withdrawal and hence indirectly impact the efficacy endpoint by causing data to be missing.

The following criteria define the protocol deviations which, if they occur prior to an analysis timepoint of interest (e.g. Month 12), will lead to exclusion of a subject from the Per-Protocol population for that analysis. Potential protocol deviations leading to exclusion from PP population will be reviewed by the study team to confirm that they meet these criteria. A final review will occur before the clinical database has been frozen for analysis.

A subject meeting any of the following criteria will be excluded from the Per Protocol population based on case-by-case clinical determination:

Number	Exclusion Description
01	Participant deviates from any inclusion or exclusion criteria that may significantly affect exposure, response to therapy or participant safety or that are fundamentally inconsistent with the intended study population, as recorded in the Protocol Deviation form in the eCRF based on study team review (where indicated in the PDMP as case-by-case determination).
02	Participant has maintenance phase non-compliance (including IM dosing errors) with investigational product up to an analysis timepoint of interest, meeting one of the following conditions:  1. Month 12 analysis only:  • Q2M arm: two or more injection intervals affected by over dosage deviations (e.g. extra injection or excessive volume administered, length of time between injections less than 7 weeks, excluding split doses).  2. ≥10% of total time on-treatment with under dosing deviations. The percentage of total time on-treatment with under dosing deviations will be calculated by (the total number of non-compliant dosing days / the total number of intended exposure days) * 100%.  Number of Intended Exposure Days = Date of Last Viral Load – Start Date of Study Treatment + 1, where the last viral load refers to the last on-treatment viral load up to Study Day 360 for Q2M arm and study day of last nominal Month 12 visit for DTG + RPV arm during maintenance phase for Month 12 analysis.

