Number	Exclusion Description							
	The total number of non-compliant dosing days up to the analysis timepoint visit (or date of IP discontinuation/withdrawal, whichever is earlier), is derived as follows (summing across all instances):  • Q2M arm:							
	
 
Length of time (in days) until next injection from date of dosage deviation (e.g. 2 mL administered instead of 3 mL).
 
Length of time (in days) in excess beyond 67 days between injections.
 
Length of time (in days) in excess beyond 67 days from last injection until start of oral bridging post Month 4.
 
Interrupted days in oral bridging if the oral dose has been interrupted for 3 or more consecutive days and the primary interruption reason is not adverse event or laboratory abnormality (based on the eCRF Exposure forms). 3 days will be assumed if such interrupted days are not available in the database.
 
DTG + RPV arm: Durations of interruptions for reasons other than treatment-related adverse events or laboratory abnormalities (based on
 
							
	Exposure eCRF forms).							
03	Prohibited medications: receiving ART medication other than that prescribed/allowed by the study (excluding permanent changes in ART regimen; such cases will be retained as 'HIV1-RNA ≥50 c/mL' in the per protocol snapshot analysis) or receiving prohibited concomitant medication that would impact exposure or response to therapy with duration and route of administration taken into consideration, as recorded in the Protocol Deviation form in the eCRF based on study team review (where indicated in the PDMP as case-by-case determination).							
04	Permanent discontinuation of IP/withdrawal due to a reason of "Protocol Deviation" (as recorded in the eCRF).							
05	Other important protocol deviations that exclude Participant from Per protocol population as recorded in the Protocol Deviation form in the eCRF based on study team review (where indicated in the PDMP as case-by-case determination).							

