#### **Detailed steps**

Please note that the following scenarios will NOT be penalized Per Snapshot algorithm (i.e. please exclude these scenarios from **Condition** 1-4).

 Dose reduction, dropping a component, or change in formulation (e.g. 'Tivicay + Kivexa' to 'Triumeq' with the identical ingredients)

Condition ('Month 12' indicates Month 12 window)	Response	Reasons
If non-permitted change in background therapy prior to Month 12	HIV1-RNA ≥ 50	Change in background therapy
2. If permitted change [a] in background therapy prior to Month 12 AND the latest on-treatment VL prior to/on the date of change is ≥ 50 c/m (NA to this study)	HIV1-RNA ≥ 50	Change in background therapy
3: If non-permitted change in background therapy		

\* Note: since changes in ART are not permitted in this protocol, all such subjects who change ART during the maintenance phase and prior to an analysis timepoint will be considered 'HIV1-RNA ≥ **50** copies/mL'. Participants with protocol permitted oral bridging treatment will not be considered 'HIV-1 RNA ≥ 50 c/mL' due to 'change in ART'.

during	Month 12		
	Last on-treatment VL during Month 12 prior to/on the date of change ≥ 50 c/mL	HIV1-RNA ≥ 50	Data in window not below 50
	Last on-treatment VL during Month 12 prior to/on the date of change <50 c/mL	HIV1-RNA < 50	
	No VL during Month 12 prior to/on the date of change	HIV1-RNA ≥ 50	Change in background therapy
Month 1	mitted change [a] in background therapy during 2 AND the last on-treatment VL prior to/on the change is ≥ 50 c/mL (NA to this study)		
4.1	this last on-treatment VL occurs prior to Month 12	HIV1-RNA ≥ 50	Change in background therapy
	this last on-treatment VL occurs during Month 12 but prior to/on the date of change	HIV1-RNA ≥ 50	Data in window not below 50
5: If non	e of the above conditions met		
5.1	VL available during Month 12		
	Last on-treatment VL during Month 12 ≥ 50 c/mL	HIV1-RNA ≥ 50	Data in window not below 50
	
 
Last on-treatment VL during Month 12 <50 c/mL
 
	HIV1-RNA < 50	
5.2	No VL during Month 12		

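### Per-protocol dosing rule (SAP 12.1.1, criterion 02): the between-injection count has no bridging exemption, so read literally one full bridged cycle at Month 4, 6, 8 or 10 passes the 10% under-dosing limit

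*SAP*

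**What the plan says.** The under-dosing limb of criterion 02 is "≥10% of total time on-treatment with under dosing deviations". The denominator is "Number of Intended Exposure Days = Date of Last Viral Load – Start Date of Study Treatment + 1", where for the Month 12 analysis the last viral load is "the last on-treatment viral load up to Study Day 360 for Q2M arm". The numerator is "The total number of non-compliant dosing days up to the analysis timepoint visit", or up to discontinuation or withdrawal if that is earlier. For the Q2M arm it sums every instance of four components:

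1. days from a dosage deviation until the next injection;
2. "Length of time (in days) in excess beyond 67 days between injections";
3. "Length of time (in days) in excess beyond 67 days from last injection until start of oral bridging post Month 4";
4. days off oral drug during bridging, where the gap is at least three consecutive days and the main reason is not an adverse event or laboratory abnormality.

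The over-dosing limb of the same criterion carries a written exception for split doses. Component 2 carries none.

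Elsewhere, Protocol 6.7.1.1 lists bridging among permitted substitutions: in exceptional circumstances, and with the medical monitor, "Investigators may provide daily oral CAB 30 mg and RPV 25 mg as a short-term" bridge. SAP 12.9 (Appendix 9) adds that "Participants with protocol permitted oral bridging treatment will not be considered" Snapshot failures on the ground of a change in ART.

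**The concern.** Components 3 and 4 make sense only if bridging stops the clock: time counts until bridging starts, and after that only interruptions count. Component 2 has no such stop. A bridged interval is still an interval between two injections, so the same calendar days fall under contradictory rules and the results are added. Covered days are scored as under-dosing. Every component 3 day is also a component 2 day once the next injection is given, so a late start of bridging is counted twice. The same double count applies to component 4 interruptions after day 67.

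The literal reading is a realistic way to program the rule. The SAP's own adherence section (12.6.2) measures across a missed visit: when Month 8 is missed, it takes the days from the Month 6 injection to the Month 10 injection.

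At stake is who is in the per-protocol Snapshot (Table 2.02, listed under Primary Efficacy Analyses) and who appears in Table 1.07 and Listing 6 as having a deviation that led to exclusion. A participant on continuous permitted therapy could be flagged there as under-dosed.

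**Working it through.** **Inputs.** Planned interval 60 days (SAP 12.6.2, adherence). Dosing window after Month 2, ±7 days (Protocol 6.8.1.1). Target days Month 2 = 31, 4 = 91, 6 = 151, 8 = 211, 10 = 271, 12 = 331, 14 = 391 (SAP 12.3.1 formula and Table 6). Limit 10%.

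**The plan's own figure.** 60 + 7 = 67 days, which reproduces the limit in components 2 and 3.

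**Formula.** Score = 100 × non-compliant days / intended exposure days. The denominator is 331 if the last viral load is on the Month 12 target day and 360 at the cap.

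**Literal reading, one missed injection, fully bridged, resumed at the next scheduled visit:**

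| Missed | Interval | Component 2 days | Over 331 | Over 360 |
|---|---|---|---|---|
| Month 2 | 91 − 1 = 90 | 90 − 67 = 23 | 6.9% | 6.4% |
| Month 4, 6, 8 or 10 | e.g. 271 − 151 = 120 | 120 − 67 = 53 | 16.0% | 14.7% |
| Month 12, cut at Day 331 | 331 − 271 = 60 | 0 | 0% | – |
| Month 12, cut at Day 360 | 360 − 271 = 89 | 89 − 67 = 22 | 6.6% | 6.1% |

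If the last viral load falls on Day 301, the start of the Month 12 window in Table 6, the middle case is 53/301 = 17.6% and a missed Month 2 is 23/301 = 7.6%.

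**Components 3 and 4 governing bridged intervals.** With bridging started by day 67 and taken without interruption, non-compliant days = 0, so the score is 0%.

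**Interval needed to reach the limit.**
- Denominator 331: 10% is 33.1, so 34 days, and 67 + 34 = 101 days between injections.
- Denominator 360: 36 days, so 103.
- Denominator 301: 31 days, so 98.

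From a missed visit at day 60, the first two mean 41 to 43 days until the next injection. A 28-day bridge gives an interval of 88 days and 21/331 = 6.3%. These are single-bridge figures. Because instances are summed, two such bridges would give 42/331 = 12.7%.

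**Double count.** Take a missed Month 6, 8 or 10 with bridging started on day 75 and the next injection on day 120. Component 2 gives 53 and component 3 gives 75 − 67 = 8, a sum of 61, and 61/331 = 18.4%. The days actually uncovered are 8, or 8/331 = 2.4%.

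**The case against.** The best defence is that the list already contains its bridging rules. If component 2 also covered bridged intervals, component 3 would only recount days already in the total, so the coherent reading is that component 2 is for unbridged intervals and components 3 and 4 are for bridged ones. That is probably what was meant. It stands as an inference about intent, but the SAP never states it.

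Three stronger readings are tempting, and the documents do not support them:

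- A reader might infer that any bridged missed injection breaches 10%. It does not: Month 2, Month 12 and shorter single bridges stay below. Bridging is described as short-term, and under the COVID-19 appendix it lasts only until injections can resume. That appendix does, however, foresee bridging beyond two months, so a full missed cycle is not far-fetched.
- A reader might infer that the plan deliberately treats bridging as under-dosing, or contradicts the Snapshot appendix. Components 3 and 4 point the other way, and the Snapshot statement governs outcome classification, not per-protocol compliance.
- A reader might infer that these participants are removed automatically. SAP 12.1.1 provides for study-team review and case-by-case determination. But that review confirms whether cases meet these same criteria, so it inherits the overlap and leaves a computable quantity to judgement in an open-label study.

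Two further points stand. Protocol 12.10.6.1 records COVID-19 bridging as a protocol deviation, so listing it as one is right, although that does not make the days under-dosed. And the day-75 example starts later than the COVID-19 appendix expects, so it illustrates the double count and is not a typical case.

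**Conclusion.** The point holds as an overlap in the written rule. Taken literally, criterion 02 scores a full bridged cycle at Month 4, 6, 8 or 10 at about 15% to 16% (17.6% with a Day 301 denominator) when the other components imply 0%, and the 10% limit lies between the two. It also double counts late starts of bridging.

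The reach is limited. The study is descriptive, the primary summary uses ITT-E and is untouched, and only Table 2.02 and the displays of per-protocol exclusions can change. The documents do not say how many participants would be bridged for a full cycle. For scale only, with the 100 participants and 3% rate used in Protocol 10.2.1, removing one failure moves 3/100 (3.0%) to 2/99 (2.0%), while removing one non-failure gives 3/99, still 3.0%.

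The percentages assume injections on the SAP target days, a single missed injection, and counting of an open interval up to the Month 12 cut-off. A participant with an earlier last viral load has a smaller denominator and a higher score.

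**What to change.** Replace components 2 and 3 with one: *days in excess of 67 since the last injection that are not within a protocol-permitted oral bridging period, counted once until the next injection*. Keep component 4 for interruptions during bridging, and define the bridging period by its start and stop dates so that no day falls under both.

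This is better than only restricting component 2 to unbridged intervals. Component 3 applies after Month 4, so that restriction would leave an earlier uncovered gap counted nowhere. For example, with an injection on Day 31 and bridging from Day 110, if that is not regarded as after Month 4, 79 − 67 = 12 days would be lost. The single component counts them, and also counts any gap between the end of bridging and the next injection.

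State as well whether standard-of-care bridging under Protocol 12.10.3 counts as cover. SAP 2.1 refers to protocol amendment 1, and criterion 02 does not mention it. COVID-19 bridging can still be summarised as a protocol deviation without adding under-dosed days.

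The cost is a few sentences in SAP 12.1.1 and a small programming change before database freeze. Protocol 6.6 already has treatment start and stop dates recorded in the eCRF.

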## 12.2. Appendix 2: Schedule of Activities

## 12.2.1. Protocol Defined Schedule of Events for CAB LA + RPV LA Q2M Administration

Procedures Q2M	a						ı	Vionth							F
	Day 1 a	2 º	4	6	8	10	12	14	16	18	20b	22 b	24	26	WD t. m
Written Informed Consent	Х														
Demography	Х														
Eligibility Verification	Х														
Physical Exam	Х														
Medical History	Х														
Center for Disease Control and Prevention (CDC) Classification	Х														
Rapid Plasma Reagin (RPR)	Х														
Symptom Directed Physical Exam, injection site reaction (ISR) and Medical Assessment c	Х	Х	Х	Х	Х	Х	Х	Х	Х	Х	Х	Х	Х	Х	Х
Vital Signs (blood pressure [BP], heart rate [HR]) d	Х	Х	X		Х		Х		Х		Х		Х		Х

Procedures Q2M	æ						ı	Vonth							_
	Day 1 ª	2 º	4	6	8	10	12	14	16	18	20b	22 b	24	26	WD ', m
Weight, Height & body mass index (BMI)e	Х	Х	Х		Х		Х		Х		Х		Х		Х
HIV Associated Conditions, AE and serious adverse event (SAE) Assessments, Con Meds	Х	Х	Х	Х	Х	Х	Х	Х	X	Х	Х	Х	Х	Х	Х
12-Lead electrocardiogram (ECG) f	Х						Х								Х
Clinical Chemistry and Hematology	Х	Х	Х		Х		Х		Х		Х		Х		Х
Pregnancy Testing (U)rine or (S)erum g	U	U	U	U	U	U	U	U	U	U	U	U	U	U	U
HIV-1 RNA and sample for storage h	Х	Х	Х	Х	Х	Х	Х	Х	Х	Х	Х	Х	Х	Х	Х
CD4+	Х	Х	Х		Х		Х		Х		Х		Х		Х
Urinalysis	Х														Х

Procedures Q2M	в						ı	Month							_
	Day 1 ª	2 °	4	6	8	10	12	14	16	18	20b	22 b	24	26	WD i, m
Fasting Glucose, Cholesterol (Total, high density lipoprotein [HDL] and low density lipoprotein [LDL]) and Triglycerides i	X						X						Х		Х
Prothrombin time (PT)/ partial thromboplastin time (PTT)/international normalized ratio (INR)	X														Х
PK Diary (D)ispensation and (R)eview	R														
PK Sample (S)torage j	S						S								S
LA Study Intervention Administration k	Х	Х	Х	Х	Х	Х	Х	Х	Х	Х	Х	Х	Х	Х	
HIVTSQc							Χ								Х
HIVTSQs	Х			Х			Χ								Х
HIVDQoL	Х			Х			Х								Х
Preference							Х								
Reason for Switch	Х														

Procedures Q2M	rs S		Month									F			
	Day 1	2 °	4	6	8	10	12	14	16	18	20b	22 b	24	26	WD to
Participant Visit Reminder Contact	Х	Х	Х	Х	Х	Х	Х	Х	Х	Х	Х	Х	Х	Х	
Participant Contact Detail Confirmation	Х	Х	Х	Х	Х	Х	Х	Х	Х	Х	Х	Х	Х	Х	

See footnote "b" for continuation of visit schedule after Month 26. Continue until either locally approved and commercially available, the participant no longer derives clinical benefit or meets a protocol-defined reason for discontinuation or until development is terminated.

- a. The Day 1 visit will take place during Week 312 (or Week 324 in the event of unavoidable delays) of the LATTE study, the participant's last week on study. LATTE participants eligible for POLAR study dosing will take final dose of CAB 30 mg + RPV 25 mg in the clinic within 2 hours of the Q2M IM regimen. For IM dosing administration loading doses are required. (Day 1=1st loading dose; Month 2=2nd loading dose)
- b. Continue this pattern for visits for the remainder of the study. For example, Month 28 will be conducted just like Month 20, Month 30 will be conducted just like Month 22 and so on.
- c. Physical exams should be conducted as part of normal routine clinical care but data will not be collected in the electronic case report form (eCRF). Medical assessments include any decisions the study staff must make for participant management.
- d. Measure vital signs after about 5 minutes of rest in a semi-supine position.
- e. Height collected at Day 1 only.
- f. On Day 1, ECGs should be performed in triplicate at least 5 minutes apart and following 5 minutes of rest in a semi-supine position within 1 hour prior to first dose. Also on Day 1, a 2-hour post dose ECG will be performed for all participants. The 2-hour post dose ECG on Day 1 can also be used for the LATTE Week 312 (or Week 324, if needed) visit. ECG evaluations at other visits should be obtained after dosing, preferably 2-4 hours post dosing.
- g. A (-) urine pregnancy test is required prior to any injection and as required by medical monitor after a treatment interruption. A (+) urine test should be confirmed with a stat serum test. If (+), participant will need to be withdrawn.
- h. Plasma for storage samples are collected for possible future analyses, back-up in cases of loss/damage in transit and geno/pheno analyses for virologic failures.
- i. Fast overnight; however, a minimum of a 6 hour fast is acceptable.
- Take PK samples pre-dose.
- k. Q2M Injections are 1 x CAB LA 600 mg IM + 1 x RPV LA 900 mg IM. If possible, injections should be spaced approximately 2 cm from one another and from the site of any previous injection and or any injection site reaction. Bring RPV LA to approximately room temperature prior to injecting. Time and location of injection (right or left) as well as needle length used will be collected in the eCRF. IM dosing is expected to occur during the month in which the participant's projected visit falls (as according to the Day 1 visit). An additional (+ or -) 7day window from date of projected visit is stipulated for IM dosing. All decisions regarding dose interruption/ resumption must be discussed with the medical monitor in advance.

#### 12.2.2. Protocol Defined Schedule of Events for DTG + RPV Administration

Procedures for DTG+RPV	Day 1 a	Month 3	Month 6	Month 9	Month 12	WD j	Notes
Written Informed Consent	Х						a. The Day 1 visit will take place during Week 312 (or Week 324 in the event of unavoidable delays) of the LATTE study, the
Demography	Х						participant's last week on study. LATTE participants eligible for POLAR study dosing will take final dose of CAB 30 mg + RPV 25
Eligibility Verification	Х						mg in the clinic. See Section 6.2 of the protocol for dosing administration.  b. Physical exams should be conducted as part of normal routine
Physical Exam	Х						clinical care but data will not be collected in the eCRF. Medical assessments include any decisions the study staff must make for
Medical History	Х						participant management. c. Measure vital signs after about 5 minutes of rest in a semi-supine
CDC Classification	Х						position. d. Height collected at Day 1 only.
RPR	Х						e. On Day 1, ECGs should be performed in triplicate at least 5 minutes apart and following 5 minutes of rest in a semi-supine position within 1 hour prior to first dose. Also on Day 1, a 2-hour
Symptom Directed Physical Exam and Medical Assessment b		Х	Х	Х	Х	Х	post dose ECG will be performed for all participants. The 2-hour post dose ECG on Day 1 can also be used for the LATTE Week 312 (or Week 324, if needed) visit. ECG evaluations at other
Vital Signs(BP, HR) °	Х	Х	Х	Х	Х	Х	visits should be obtained after dosing, preferably 2-4 hours post dosing.
Weight, Height & BMI d	Х	Х	Х	Х	Х	Х	f. Plasma for storage samples are collected for possible future analyses, back-up in cases of loss/damage in transit and geno/pheno analyses for virologic failures.
HIV Associated Conditions, AE and SAE Assessments, Con Meds	Х	Х	Х	Х	Х	Х	g. A (-) urine pregnancy test is required prior to any administration of drug and as required by medical monitor after a treatment interruption. A (+) urine test should be confirmed with a stat

I. Or Long-Term Follow Up

m. Follow Up Visit - Conduct ~4 weeks after the last dose of investigational product (IP) if not entering Long-Term Follow Up and only if the participant has ongoing AEs or lab abnormalities at the last on-study visit. May be conducted by telephone.

Procedures for DTG+RPV	Day 1 a	Month 3	Month 6	Month 9	Month 12	WD j	Notes
12-Lead ECG °	Х				Х	Х	serum test. If (+), participant will need to be WD. h. Fast overnight; however, a minimum of a 6 hour fast is
HIV-1 RNA	Х	Х	Х	Х	Х	Х	acceptable. i. DTG 50 mg + RPV 25 mg. Administer daily with food
CD4+	Х	Х	Х	Х	Х	Х	j. Follow Up Visit - Conduct ~4 weeks after the last dose of IP and only if the participant has ongoing AEs or lab abnormalities at the last on-study visit. May be conducted by telephone.
Plasma for Storage f	Х	Х	Х	Х	Х	Х	
PK Sample for Storage						S	
Clinical Chemistry and Hematology	Х	Х	X	Х	X	Х	
Pregnancy Testing g	U	U	U	U	U	U	
Urinalysis	Х					Χ	
Fasting: Glucose, Cholesterol (Total, HDL and LDL) and Triglycerides h	Х					Х	
PT/PTT/INR	Х					Х	
HIVTSQc					Х	Х	
HIVTSQs	Х		Х		Х	Х	
HIVDQoL	Х		Х		Х	Х	
Participant Visit Reminder Contact	Х	Х	Х	Х	Х		
Participant Contact Detail Confirmation	Х	Х	Х	Х	Х		

Procedures for DTG+RPV	Day 1 a	Month 3	Month 6	Month 9	Month 12	WD i	Notes
Study Treatment Dispensation i	Х	Х	Х	Х	Х		

